9. SUPPLY AND ACCOUNTABILITY OF INVESTIGATIONAL PRODUCT

Stocks of investigational product will be purchased directly from Baxter Healthcare. Stability of the investigational product has been confirmed for 180 days. Zeullig Pharma, a third party GMP certified pharmaceutical distributor will be contracted to mask the syringes in such a way that the solution within the syringe is visible (to ensure the correct volume and absence of air bubbles) but prevents the identification of the betamethasone suspension. Study drugs will be prepared in tamper proof packaging for each participant with the appropriate labelling corresponding to the randomisation number. Sufficient stocks will be held at each site to ensure no disruption in the trial supply, however stock quantities will be kept low as the shelf life of this product is only 180 days.

9.1 DRUG ACCOUNTABILITY

Each participating site will maintain a record of drugs dispensed for each participant and subsequent returns (eg if only a single injection is administered). Each site will also maintain a record of receipt for all study treatments and records regarding disposal of unused stock, or stock that exceeds the approved stability expiry date.

10. STORAGE OF BLOOD AND TISSUE SAMPLES

No blood or tissue samples will be collected for this study

11. DATA SECURITY & HANDLING

11.1 DETAILS OF WHERE RECORDS WILL BE KEPT & HOW LONG THEY WILL BE STORED

All hard copy data will be stored at each site by the study investigators at each site. Individual sites will be responsible for ensuring that all hard copy data are stored appropriately. All electronic data will be securely stored in a password protected database on a secure password protected server.

All data will be retained for 25 years consistent with requirements for interventional studies in pregnancy

After 25 years all paper data will be destroyed by secure shredding. All electronic data will be deleted.

11.2 CONFIDENTIALITY AND SECURITY

All participants will be allocated an individual study number. This study number will allow re-identification of patient research data. The code linking the participant identifying data with the study number will be securely stored separately to the main database. All hard copy data will be stored in a locked filing cabinet located on Level 3 of the Western Centre for Health Research Education building at Western Health which is accessible only to the study investigators. All electronic data will be securely stored in a password protected REDCap database held on a secure password protected server at The University of Melbourne. Each participating site will only have access to data from their own site. For the purposes of contacting participants for long term follow up, identifying data will be held in the central database to allow the coordinating centre to maintain follow up. Identifying data will be held in a separate database which will be linked to the research database through a unique participant identification code.

We will use social media to raise awareness of the PRECeDe Trial. This will allow some participants to identify themselves if they wish to discuss their experience of participation in this trial.

11.3 ACCESS TO DATA AND DATA SHARING

The Trial steering committee will have full access to the dataset and oversee analysis, interpretation and reporting of the final results. After 12 months following publication of the primary results of the trial, the de-identified data can be requested for use in future research provided that

- The proposed use of the data is consistent with the objectives of the PRECeDe trial;
- Researchers provided a methodologically sound research proposal;
- Appropriate data management plans are in place

12. SAFETY REPORTING

12.1 DEFINITIONS

ADVERSE EVENT (AE) is any untoward medical occurrence in a participant administered an investigational product (or placebo) and which does not necessarily have a causal relationship with this treatment. An AE can therefore be any unfavourable or unintended sign (including an abnormal laboratory finding), symptom, or disease temporally associated with the use of a medicinal investigational product, whether or not considered related to the medicinal product (see below).

Adverse events include the following:

- All suspected adverse drug reactions
- All adverse events related to the investigational product– overdose, abuse, withdrawal, sensitivity, toxicity or failure of expected pharmacological action (if appropriate)
- Apparently unrelated illnesses, including the worsening (severity, frequency) of pre-existing illnesses
- Injury or accidents.
- Abnormalities in physiological testing or physical examination that require clinical intervention or further investigation (beyond ordering a repeat examination)

- Any untoward event that occurs after the protocol-specified reporting period which the Investigator believes may be related to the drug or device.

AEs are not required to be reported unless they meet SUSAR (see below) and/or Outcome criteria.

SERIOUS ADVERSE EVENT (SAE) is any serious untoward medical occurrence. In this trial, the following will be considered as serious adverse events:

- Maternal death
- Neonatal Death
- Fetal Death (stillbirth)
- Maternal admission to intensive care unit
- Maternal life threatening event
- Maternal ketoacidosis
- Maternal hypoglycaemia associated with seizures or loss of consciousness within the first 7 days following the birth
- Neonatal hypoglycaemia associated with seizures or loss of consciousness within the first 7 days following the birth
- Maternal persistent or significant disability or incapacity
- other important medical events which, in the opinion of the investigator, are likely to become serious if untreated (including unplanned admission of the mother prior to CS)
- Readmission of the mother or baby following discharge from hospital

NOTES:

(i) The term “life-threatening” in the definition of “serious” refers to an event in which the patient was at risk of death at the time of the event; it does not refer to an event which hypothetically might have caused death if it were more severe.

(ii) Important medical events which may not be immediately life-threatening or result in death or hospitalization but which may jeopardize the patient or may require intervention to prevent one of the listed outcomes in the definition above should also be considered serious.

(iii) Note that admission to hospital for birth is not regarded as an SAE. Admission to hospital for >24 hours prior to CS birth is not regarded as an SAE if this is standard practice for women with diabetes (including those who receive corticosteroids) at the site, however unplanned admission to hospital prior to birth, or readmission following discharge from hospital after birth will be regarded as an SAE.

A SUSPECTED UNEXPECTED SERIOUS ADVERSE REACTION (SUSAR) is an SAE that

- is related to the drug and is unexpected (i.e. not listed in the investigator brochure or approved Product Information; or
- is not listed at the specificity or severity that has been observed; or
- is not consistent with the risk information described in the Patient Information and Informed Consent Form or elsewhere in the protocol. (FDA, Safety Reporting Requirements for INDs and BA/BE Studies, draft guidance, September 2010).

An event is causally related if there is a reasonable possibility that the drug caused the AE, i.e. there is evidence to suggest a causal relationship between the drug and the event (FDA, Safety Reporting Requirements for INDs and BA/BE Studies, draft guidance, September 2010).

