5.1 STUDY TYPE & DESIGN & SCHEDULE

The PRECeDe Randomised Trial is an international multicentre, randomised, triple blind, placebo controlled trial (Figure 4).

Trial setting: The trial will be conducted in maternity units throughout Australia and New Zealand

Trial entry: Women will be identified and counselled by trained research midwives. Written consent will be obtained. In accordance with the CONSORT statement⁶⁰ we will collect data regarding the number of eligible participants, the number approached, and the number of participants who decline to take part in the trial via a waiver of consent to collect deidentified data regarding potentially eligible participants.

Randomisation: Eligible, consenting women will be randomised using a computer generated random number sequence. The randomisation schedule, using a 1:1 randomisation and variable block size will be prepared in advance.

Randomisation will be stratified by:

- Type of diabetes (Type 1 diabetes, Type 2 Diabetes, Gestational Diabetes)
- Gestation at delivery (35⁺⁰ to 36⁺⁶ and 37⁺⁰ to 38⁺⁶ weeks, 39⁺⁰ to 39⁺⁶ weeks)
- Recruiting site

Randomisation can only take place within 7 days prior to planned elective CS and at least 24 hours prior to planned elective CS to allow two doses of betamethasone to be administered prior to birth. Randomisation can occur within the week prior to 35⁺⁰ weeks gestation as long as the planned CS is scheduled after 35⁺⁰ weeks gestation.

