Treatment Allocation: Assignment is to either the 'betamethasone group' or the 'placebo group'. A study number will be allocated to the participant that corresponds to the relevant trial treatment pack, each of which look identical and contain two masked syringes each containing either 11.4 mg of Celestone Chrondose in 2 ml (betamethasone 11.4 mg, as betamethasone sodium phosphate and betamethasone acetate) or placebo (normal saline 2 ml), both of which will be supplied and packaged by Baxter Healthcare Corporation who have confirmed stability testing for both the active drug and placebo for 180 days. Syringes will be masked with red tape to ensure that the volume of contents can be assessed but the betamethasone suspension will not be distinguished from the clear solution of the placebo. The syringes will be packaged with the appropriate randomisation number by Zeullig Pharma. All drugs will be prescribed by a medical practitioner as "Betamethasone 11.4mg in 2 ml, x2 doses or Normal Saline Placebo 2 ml, x 2 doses" and dispensed by Pharmacy staff at the recruiting site according to the allocated randomisation number.

Treatment schedules: Women in both treatment groups will be given the contents of one of their allocated syringes intramuscularly at least 24 hours prior to the planned CS. The second injection will be retained at the site and administered 24 hours (\pm 4 hours) later. Researchers, participants and staff will be blinded to the treatment allocation. If birth is required less than 24 hours after the first injection (for example, if the CS time must be brought forward due to maternal or fetal issues (eg spontaneous onset of labour), the second injection will be withheld. The reasons for not administering the second injection will be recorded on the CRF. The second injection should not be given earlier than 20 hours after the first injection. Failure to administer the second injection does not constitute withdrawal from the trial. There is no minimum amount of time required between the second injection and the CS.

If the CS is delayed beyond 7 days following administration of the two injections, repeat study medication (or antenatal corticosteroids) should not be administered.

Standard Care: Care for both groups will otherwise be according to standard practice for women with diabetes and their infants.

Monitoring of maternal blood sugars and treatment of maternal hyperglycaemia

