All participants will be instructed to monitor their blood glucose using a capillary blood glucose monitor prior to every meal and 2 hours following meals for 72 hours after the first injection. Participants will be asked to record all blood glucose readings via REDcap with the link provided at the time of randomisation. Women who normally use continuous glucose monitoring or flash glucose monitoring should be advised to use capillary blood glucose monitoring according to the above schedule during this time period in addition to their continuous or flash blood glucose monitor. All participants will be provided with a site specific information sheet which will provide information about target blood sugars and what to do in the event of hypoglycaemia or hyperglycaemia. Women who experience hyperglycaemia will be advised to contact

the relevant staff at the participating site for advice regarding insulin titration. Maternal hyperglycaemia will be managed in accordance with local protocols with the aim being to ensure euglycaemia as much as possible. Staff who provide advice regarding the management of hyperglycaemia will be encouraged not to disclose whether they suspect the participant receive bethamethasone or placebo. Guidance regarding insulin management is provided in the PRECeDe Insulin Management Guideline (see Appendix 2) however relevant staff at each site will be responsible for individualising the care.

While, there is no requirement for women who are otherwise well to be admitted during the period between randomisation and the CS, individual sites may choose to arrange routine admission for close surveillance if that is their usual practice. Admission for close surveillance is recommended in the event of significant maternal hyperglycaemia or hypoglycaemia.

Monitoring of neonatal blood glucose and treatment of neonatal hypoglycaemia

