16. APPENDIX

Appendix 1: List of Attachments included:

Document Name	Version Number	Date (e.g., 18 January 2012)
Patient Information Consent Form Master	2	4 th August 2022
Patient Symptoms Questionnaire	1	11 May 2022
Participant Instructions Following Injections	2	8 th August 2022
AQoL8D	12	23 March 2017
Edinburgh Postnatal Depression Score (EPDS)		
SF12	2	30 June 2002
Postnatal Questionnaire	1	8 August 2022
PRECeDe CRF 0	1	2 May 2022
PRECeDe CRF 1	1	2 May 2022
PRECeDe CRF 2	1	2 May 2022
PRECeDe CRF 3	1	2 May 2022
PRECeDe CRF 4	1	2 May 2022
PRECeDe CRF 5	1	2 May 2022
PRECeDe CRF 6	1	2 May 2022
PRECeDe CRF 7	1	2 May 2022
PRECeDe CRF 8	1	2 May 2022
PRECeDe CRF 9	1	2 May 2022
PRECeDe CRF 10	2	12 August 2022
PRECeDe CRF 11	1	2 May 2022
PRECeDe CRF 12	1	2 May 2022
PRECeDe Blood Sugar Diary Master	1	11 May 2022
PRECeDe Poster Master	1	11 May 2022

CS Weekly Screening Log	1	11 May 2022
PRECeDe Safety Monitoring Committee Terms of Reference	1	22 August 2022
PRECeDe Data Monitoring Committee Terms of Reference	1	22 August 2022

Appendix 2: Management of hyperglycaemia between study drug injection and elective caesarean section – Guidance for Staff providing insulin titration advice

Blood Glucose (BGL) monitoring:

- BGL monitoring should occur fasting, 2 hours after breakfast, before lunch, 2 hours after lunch, before dinner and 2 hours after dinner
- The target BGLs are ≤ 5.0 mmol/L fasting and < 6.7 mmol/L 2 hours after meals or according to local hospital protocols
- Notify the designated staff if hypoglycaemia (BGL < 3.5 mmol/L) or hyperglycaemia with BGL > 8 mmol/L

Hypoglycaemia

- In women with GDM, manage hypoglycaemia if BGL < 3.5 mmol/L
- In women with pre-gestational type 1 or type 2 diabetes, manage hypoglycaemia if BGL < 4.0
- If hypoglycaemia persists despite treatment, consider fetal well being assessment according to local hospital protocols.

Blood ketone level checks:

- Consider checking blood ketone levels if BGL > 10.0 – especially in patients with Type 1 diabetes

Additional Insulin

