In addition to the diabetes management regimen prior to administration of trial medication, consider supplemental sliding scale of short-acting subcutaneous insulin (e.g. Novorapid®) in the event of hyperglycaemia. Dose adjustments are at the discretion of clinical staff at the participating site and should take into account the participant's type of diabetes and diabetes management. Advice should be individualised with the aim being to ensure euglycaemia without disclosing whether the staff member suspects the participant received betamethasone or placebo.

[figure not shown]
- Participant should be advised to contact a nominated member of staff at the site (eg endocrinologist, obstetric physician, diabetes educator) if there are two results above the target BGLs of ≤ 5.0 mmol/L fasting or < 6.7 mmol/L 2 hours after meals OR if there is a single result more than 8.0 mmol/L
- If pre-prandial blood glucose is between 8.1-10 mmol/L, 2 extra units of short-acting insulin should be administered.

- If pre-prandial blood glucose is between 10.1-12 mmol/L, 4 extra units of short-acting insulin should be administered.
- If pre-prandial blood glucose is between 12.1-14 mmol/L, 6 extra units of short-acting insulin should be administered.
- If pre-prandial blood glucose is between 14.1-16, 8 extra units of short-acting insulin should be administered.
- If pre-prandial blood glucose is greater than 16, 10 extra units of short-acting insulin should be administered.

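### The only named SAE item for severe maternal hypoglycaemia starts at birth, so before birth the same event is captured only through general criteria or an unplanned admission

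*Protocol*

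**What the plan says.** The SAE list in Protocol section 12.1 has one entry that names maternal hypoglycaemia: "Maternal hypoglycaemia associated with seizures or loss of consciousness within the first 7 days following the birth". The entry for the baby has the same qualifiers and the same window: "Neonatal hypoglycaemia associated with seizures or loss of consciousness within the first 7 days following the birth". Maternal ketoacidosis, in the same list, has no time limit.

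Section 5.1 places the study treatment before birth. "Randomisation can only take place within 7 days prior to planned elective CS and at least 24 hours prior to planned elective CS". The first syringe is given "intramuscularly at least 24 hours prior to the planned CS", and the second about a day later. Participants measure capillary glucose "prior to every meal and 2 hours following meals for 72 hours after the first injection".

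Appendix 2 is headed "Management of hyperglycaemia between study drug injection and elective caesarean section". For that interval it tells staff to "consider supplemental sliding scale of short-acting subcutaneous insulin" if glucose is high. It also sets thresholds for managing low glucose and adds: "If hypoglycaemia persists despite treatment, consider fetal well being assessment". The Protocol therefore foresees maternal hypoglycaemia before birth.

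**The concern.** A window that begins at birth suits the neonate, who can only have this event after birth. For the mother it begins after the injections and after the period for which Appendix 2 was written. A hypoglycaemic seizure or loss of consciousness on the day after an injection, with the baby undelivered, does not meet the one item that names it. A site could even read the explicit postnatal window as a deliberate exclusion of the antenatal event.

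What is at stake is the completeness of what the Safety Monitoring Committee and the Data Monitoring Committee see. Section 12.2 requires SAEs to be reported within 3 days. Below SAE level there is little to catch the event. Section 12.1 does not require an adverse event to be reported unless it meets SUSAR or outcome criteria, and a SUSAR must itself be an SAE.

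**Working it through.** No sample size, power or event count is involved. The check sets the window of the named item against the schedule, and then goes through the other ways in which a pre-birth event could become an SAE.

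**1. Window against schedule.** Inputs: the named item begins at birth (12.1), the first injection is at least 24 h before the planned caesarean (5.1), and monitoring lasts 72 h from the first injection (5.1). Let T be the hours from first injection to birth.

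- Pre-birth hours covered by the named item: 0 of T, whatever T is.
- Share of the monitoring period before birth, and so outside the item: min(T, 72) / 72.

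| T | Monitored hours before birth | Share outside the named item | Monitored hours after birth |
|---|---|---|---|
| 24 h | 24 | 24/72 = 33% | 48 |
| 48 h | 48 | 48/72 = 67% | 24 |
| 72 h or more | 72 | 72/72 = 100% | 0 |

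The Protocol does not give the distribution of T. The 7-day limit in 5.1 applies to randomisation, not to injection. It bounds the scheduled T only because injection follows randomisation.

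**2. Other SAE routes open before birth (12.1 and its notes).**

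- *Maternal death, stillbirth, intensive care admission, lasting disability.* These have no time limit, but each needs a further outcome beyond the seizure or loss of consciousness.
- *Life-threatening event.* No time limit. Note (i) requires that the woman was at risk of death at the time. A brief episode that was promptly treated may be judged not to qualify.
- *Important medical event.* The list item rests on the investigator's opinion. Note (ii) says that events which may endanger the patient or need intervention to avert a listed outcome should be treated as serious. It has no time limit, but applying it takes judgement.
- *Unplanned admission before birth.* Under note (iii) this is an SAE, and 5.1 recommends admission for significant maternal hypoglycaemia. For a woman at home this is a concrete trigger. It does not work for a woman already in hospital: 5.1 lets sites admit routinely, and note (iii) exempts stays that are standard practice at the site. It also misses an event treated without admission.

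**3. Is SAE reporting meant to cover the time before birth?** Yes. Section 12.2 asks each report to state the action taken on study treatment, including whether the second dose was given or withheld. That can only concern events before birth.

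**4. What remains.** The residual gap is a pre-birth event in a woman already admitted by routine, or not admitted at all, that the site judges neither life-threatening nor an important medical event. The Protocol gives no figure from which to size that group.

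**The case against.** The strongest reply is that nothing is truly lost. The SAE definition is broad, note (ii) fits a hypoglycaemic seizure readily, and for outpatients the recommendation to admit makes the event an SAE through note (iii). Maternal glycaemia is also recorded elsewhere. Readings are entered in REDCap for 72 h, glucose and insulin data are collected from the first dose through the post-birth visit, the side-effects questionnaire asks about hypoglycaemia, and both additional insulin and admission between randomisation and caesarean are secondary outcomes. The Protocol itself names hyperglycaemia as the maternal glycaemic risk of the drug, and its severe form, ketoacidosis, is an SAE without a window.

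Much of this stands. A reader might infer that the whole period from injection to caesarean lies outside the SAE definition. It does not: it lies outside one item. But the general routes depend on judgement or on an unplanned admission, and the routine data sources do not carry the 3-day reporting of section 12.2. They complement a named SAE criterion but do not replace it.

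A reader might also infer that the comparison of maternal safety between arms is biased. The documents do not show this. The same definition applies to both arms, so under-reporting would lower the counts, and differential capture would need a further reason. The pilot gives some ground for caution, since agreement between guessed and true allocation was 0.69 for participants and 0.84 for midwives giving or checking the drug (Table 2). Discretionary reporting could therefore be influenced by a guess at allocation. That is a possibility without a known direction or size.

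**Conclusion.** The point holds as a mismatch between one reporting window and the exposure period. The named item for severe maternal hypoglycaemia covers none of the time from first injection to birth, and so misses between 33% and 100% of the 72-hour monitoring period for births 24 hours or more after the first injection. Before birth the event reaches the committees only through general criteria or an unplanned admission. SAE capture may therefore be incomplete and differ between sites and investigators.

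The size in events is unknown, because the Protocol gives no frequency for this event and no distribution of the injection-to-birth interval. Applying a 7-day exposure to all 2200 women would not be supported: 7 days is the limit from randomisation, and half the women receive placebo. It is plausible that the maternal window was carried over from the neonatal line, but the document cannot show it. The primary outcome and its analysis are unaffected. The correction is still worth making by amendment, because the harm is one that the Protocol foresees and the change is small.

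**What to change.** In section 12.1, let the maternal hypoglycaemia item run from randomisation (or from first injection) to 7 days after birth, and state that it applies whether or not the woman is already an inpatient. Starting at randomisation would match the secondary outcomes in section 4 that already count from that point, such as maternal infection and hospital admission. Leave the neonatal item unchanged. Check that CRF 10 has the same window; the form is listed in Appendix 1 (version 2) but not shown, so it may or may not need editing.

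The cost is a one-line amendment, possibly a matching edit to the form, and a few more SAE reports for the Safety Monitoring Committee. The change concerns reporting only and alters no treatment or glucose-management rule.

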Babies born to women with pre-gestational^{7,9,19} or gestational^{9,20} diabetes also have increased rates of neonatal respiratory morbidity even after adjusting for gestational age at birth, with infants whose mothers have Type 1 or Type 2 diabetes having a 2.5 fold⁷ and 1.7 fold⁹ increase in rates of neonatal respiratory distress, respectively. Likewise, a New Zealand study demonstrated that 50% of infants born to women with Type 2 Diabetes between 33 and 39 weeks experienced neonatal respiratory distress.¹⁹ While the reasons for this are not fully understood, fetal hyperinsulinaemia, demonstrated by elevated umbilical cord c-peptide levels, is consistently reported in association with maternal gestational²¹ and pre-gestational diabetes.²² Several studies have suggested that this fetal hyperglycaemia and hyperinsulinaemia leads to a delay in maturation of the surfactant producing Type-II alveolar cells in the lungs of infants born to women with diabetes.²³⁻²⁵ In addition, fetal hyperinsulinaemia is thought to mediate the fetal cardiac hypertrophy which is often observed during pregnancies complicated by diabetes,²⁶ and can contribute to left ventricular outflow obstruction, poor cardiac output and congestive cardiac failure after birth; a combination that also contributes to neonatal respiratory distress.²⁶ Women with diabetes have significantly greater rates of pregnancy complications including increased rates of stillbirth and pre-eclampsia,⁹ so birth is frequently recommended prior to 39 weeks and is often required much earlier in the presence of pregnancy complications.^{27,28} Earlier birth potentially compounds the risks of respiratory morbidity in these infants.

Neonatal Hypoglycaemia

Neonatal hypoglycaemia is commonly defined as a blood glucose concentration below 2.6 mmol/litre.²⁹ There is a well-established relationship between symptomatic neonatal hypoglycaemia and neonatal seizures,³⁰ brain injuries detectable with MRI, and poor neurological outcomes.³¹ Even transient and mild hypoglycaemia that responds to treatment may still be associated with poorer neurocognitive³² outcomes, and poorer academic performance at school age.³³

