3.3 HYPOTHESIS

The overarching hypothesis is that administration of corticosteroids to pregnant women with either pre-gestational or gestational diabetes within 7 days prior to planned CS where CS is scheduled between 35⁺⁰ weeks and 39⁺⁶ gestation will reduce the incidence and severity of neonatal respiratory morbidity without adverse short-term (within the first 6 weeks) consequences for the mother or baby.

Specifically, we hypothesise that administration of corticosteroids to women with pre-gestational or gestational diabetes within 7 days prior to planned CS, where CS is scheduled between 35⁺⁰ weeks and 39⁺⁶ gestation, will:

1. reduce the incidence and severity of neonatal respiratory morbidity.
2. not increase the incidence of neonatal hypoglycaemia.
3. not increase the incidence of maternal morbidity (hyperglycaemia, chorioamnionitis, endometritis, or wound infection).
4. increase breast feeding rates at hospital discharge and 6 weeks post-partum.
5. reduce health care costs.

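### Section 12.1 words the life-threatening, disability and intensive-care SAE items for the mother only and sets no age limit on infant death, so some serious non-fatal infant events depend on interpretation to be reported

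*Protocol*

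**What the plan says.** Protocol section 12.1 opens with a one-line definition of an SAE that is not tied to mother or infant, then lists what will count as an SAE in this trial. Three items carry the word maternal and have no infant equivalent: "Maternal admission to intensive care unit", "Maternal life threatening event" and "Maternal persistent or significant disability or incapacity".

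The items that name the fetus or infant are stillbirth, "Neonatal Death" and "Neonatal hypoglycaemia associated with seizures or loss of consciousness within the first 7 days following the birth". Readmission after discharge is listed for mother or baby. A further item covers other important medical events that the investigator thinks would become serious without treatment; its one example is an unplanned maternal admission.

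Two notes matter. Note (i) defines life-threatening in terms of the patient. Note (ii) also counts as serious an event that may endanger the patient, or that may need intervention to prevent one of the listed outcomes.

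Section 12.1 further says that an adverse event need not be reported unless it meets SUSAR or outcome criteria, and it defines a SUSAR as a kind of SAE. Section 12.2 sends SAEs and SUSARs to the Safety Monitoring Committee within 3 days. The overarching hypothesis in section 3.3 is a benefit "without adverse short-term (within the first 6 weeks) consequences for the mother or baby".

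**The concern.** The drug is given to the mother for the sake of the infant, and the primary outcome in section 4 is measured in the infant. One would expect the infant's seriousness criteria to be at least as complete as the mother's. Because one item says mother or baby and others say maternal, a site will reasonably read maternal as a restriction.

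The gap would pass down the reporting chain. An infant event that is not recognised as an SAE cannot become a SUSAR, even if it is unexpected and thought to be drug-related. If it is not a trial outcome either, section 12.1 does not require it to be reported. At stake are prompt and uniform notice of infant harm to the Safety Monitoring Committee and the completeness of the SAE tables by arm that section 13.2 has the Data Monitoring Committee review. The primary analysis is not affected.

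**Working it through.** No power or sample-size figure is involved. The check sets the list against the rest of the protocol.

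**1. The 11 listed items by person**

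| Item in section 12.1 | Mother | Fetus or infant |
|---|---|---|
| Death | named | stillbirth named; neonatal death named, no age limit |
| Life-threatening event | named | none |
| Intensive-care admission | named | none |
| Persistent or significant disability | named | none |
| Ketoacidosis | named | none |
| Hypoglycaemia with seizures or loss of consciousness | named | named |
| Readmission after discharge | named | named |
| Other important medical events | not restricted | not restricted |

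Mother only: death, life-threatening event, intensive care, disability, ketoacidosis, hypoglycaemia = 6. Fetus or infant only: stillbirth, neonatal death, hypoglycaemia = 3. Both: readmission = 1. General: 1. Total 6 + 3 + 1 + 1 = 11.

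Named non-fatal items for the mother: 6 − 1 (death) + 1 (readmission) = 6. For the infant: 3 − 2 (stillbirth, neonatal death) + 1 (readmission) = 2. Of the life-threatening, intensive-care and disability items, 0 of 3 name the infant.

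**2. An infant event in the birth admission.** Take a baby who survives sepsis, encephalopathy or a seizure without hypoglycaemia. The baby has not died, is not hypoglycaemic and has not been readmitted, so no named item fits. The infant outcomes in section 4 are hypoglycaemia, nursery admission and stay, and respiratory measures; none of these diagnoses is among them. Nor is cardiac failure, although section 3.2 says that cardiac hypertrophy in these pregnancies can contribute to "poor cardiac output and congestive cardiac failure after birth".

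**3. The routes that remain**
- *Opening definition.* It can include the infant, but gives no criterion for serious beyond the list and notes.
- *Investigator-opinion item.* It can include the infant, but is worded for events that may become serious, not for those that already are.
- *Note (ii), prevention route.* Neonatal death is a listed outcome, so an infant event treated to prevent death can qualify, if the patient includes the baby. Infant disability does not qualify this way, because the only disability listed is maternal.
- *Note (ii), endangerment route.* This again turns on who the patient is, and it is not a disability criterion.

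The protocol does not settle who the patient is. The synopsis gives the planned subjects as mothers and their infants, but section 12.1 defines an adverse event in someone given the product, and the blinding assessment in section 5.1 speaks of the participant and, separately, her baby.

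**4. Infant death.** The hypothesis runs to 6 weeks. The protocol does not say up to what age a death is neonatal, so it is not stated whether the item covers the whole window.

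**The case against.** The strongest reply is note (ii). It says such events should be considered serious, without appeal to the investigator's opinion. Since neonatal death is listed, a baby treated for severe sepsis or cardiac failure to avert death arguably meets it. This stands in part. It rests on reading the patient as including the baby, and it leaves infant disability out. Read broadly, it could also turn much respiratory support into SAEs, which is another way for sites to diverge.

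A reader might infer that serious infant harm as a whole lies outside the list. The protocol does not support that: stillbirth, neonatal death, symptomatic hypoglycaemia and readmission of the baby are named.

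A reader might also infer that infant events reach the committees only if a site chooses. That too goes too far. Nursery admission, respiratory support and air leak are recorded as outcomes, and infant medications are recorded to discharge (section 5.1). The Data Monitoring Committee reviews aggregate events by arm, and both committees may seek further analyses (sections 13.2 and 13.3). A sick infant would leave a trace, though without its diagnosis and not as a 3-day report.

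A third inference is that infant deaths late in the 6 weeks go uncounted. That needs an assumed meaning of neonatal, such as the first 28 days, and a death without readmission. Such a death would still fit the opening definition. What stands is only that the age limit is unstated.

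Finally, the specific safety hypotheses in section 3.3 concern neonatal hypoglycaemia and listed maternal morbidities, which are measured as outcomes and do not depend on the SAE list. That is correct. The point concerns safety reporting, not those comparisons.

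**Conclusion.** The point holds in a limited form. Three seriousness items are worded for the mother alone, and infant death has no stated age limit. Non-fatal life-threatening or disabling infant events in the birth admission therefore depend on the general definition, the investigator-opinion item or note (ii) to reach 3-day reporting and SUSAR classification. Disability is the clearest omission, because note (ii) does not reach it.

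The size can be given only as coverage: 0 of 3 such items name the infant, and 2 named non-fatal items apply to the infant against 6 for the mother. The protocol gives no rate for the events concerned, so the number that might be missed cannot be estimated.

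The conclusion assumes that sites take the list as worded, and that CRF 10 and the committees' terms of reference, which Appendix 1 lists but which are not shown here, do not already name the infant criteria. The change is worth making; no efficacy result depends on it.

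**What to change.** In section 12.1:
- Reword two items as 'Life-threatening event in the mother or infant' and 'Persistent or significant disability or incapacity in the mother or infant'.
- State that notes (i) and (ii) apply to the infant as well as the mother.
- Replace the neonatal death item with infant death up to 6 weeks after birth, matching section 3.3.
- To limit volume, state that respiratory support already recorded as a trial outcome need not also be reported as an SAE unless it is fatal or suspected to be drug-related.

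An infant intensive-care item is not needed. Nursery admission is already an outcome and is frequent (44% of unexposed infants in Table 1), so such an item could bring many reports and add little.

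The respiratory exemption leaves some judgement to the investigator, but only for events that are captured as outcomes in any case.

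The cost is a wording amendment, a check that CRF 10 agrees with it, and a small number of extra infant reports for the Safety Monitoring Committee. Treatment, sample size and analysis do not change.
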